**IRB00056413**

**NCT03929367**

**Version Date: 6/11/2019**

## BACKGROUND

A large body of evidence in animals and in humans suggest that oxytocin can produce analgesia to experimental pain stimuli and relieve pain in acute and chronic clinical pain states. For the past 8 years we have, under an NIH MERIT award, tested the role of the spinal cord in oxytocin's actions by studies in rodents and clinical trials, 3 of which are ongoing, of spinally injected oxytocin.

The Pain Mechanisms Laboratory at Wake Forest is now in the process of assembling an NIH program project grant (P01) on the topic of oxytocin sites, mechanisms, and clinical applications for analgesia, and [name] will lead the clinical project in that proposal. This IRB protocol is meant to obtain preliminary data critical to that NIH application in September, 2019.

Determining the site(s) of action of oxytocin for analgesia in humans is critical to future clinical trials and drug development. We will propose to use computer-controlled intravenous infusions of oxytocin to rapidly achieve and maintain targeted plasma concentrations. By locking plasma concentrations and examining a wide concentration range, coupled with testing aimed to measure activity of oxytocin on peripheral nerves, in the spinal cord, and in the brain, we plan to identify infusion regimens that only target 1 or 2 of these sites for clinical trials.

## WHY WE NEED TO DEFINE PHARMACOKINETICS OF OXYTOCIN

In this IRB protocol we take the necessary first step towards computer-controlled intravenous infusions of oxytocin. In this protocol we will describe the pharmacokinetics of intravenous oxytocin in healthy non-pregnant adult men and women. We cannot program infusion devices for targeted concentrations without knowledge of oxytocin's pharmacokinetics in this population of interest. Although much is known of the pharmacodynamics of intravenous and intramuscular oxytocin to cause uterine contraction during pregnancy and in the postpartum period, we know virtually nothing about oxytocin's pharmacokinetics in this setting and nothing in the nonpregnant population. This reflects the fact that immunoassays used to measure oxytocin for the past 3 decades suffer critical limitations because the antibodies used are confounded by binding to oxytocin degradation products, particularly those that are tightly bound to

circulating proteins and presenting a large background of antigenicity to which these antibodies bound. In a recent review of the state of our lack of knowledge regarding oxytocin disposition, it was noted that reports differ in resting and infused oxytocin concentrations in plasma by 2 to 3 orders of magnitude, and that the use of these assays essentially generate random numbers with no basis in reality [8].

Beginning in 2016 reports appeared of highly sensitive and specific assays of oxytocin in plasma and other biofluids using liquid chromatography coupled with mass spectroscopy (LC-MS) [2; 3; 6; 11]. A recent report included pharmacokinetics of oxytocin after intramuscular injection using LC-MS [3] with concentrations assayed by a commercial entity (Syneos Health, Princeton, NJ). We have secured a quote from this company and will use them to measure oxytocin in de-identified samples from this protocol sent to their facility. We note that pharmacokinetics from intramuscular administration cannot alone inform computer controlled infusion of intravenous oxytocin, necessitating data from this IRB protocol.

#### **RATIONALE FOR OTHER MEASURES BEYOND BLOOD SAMPLES IN THIS PROTOCOL**

Although the primary goal of this protocol is to model change in oxytocin concentrations in plasma after intravenous administration, we will also acquire tests of sensory function that could be modulated by oxytocin during later time periods when blood samples are widely separated by time. There are two measures which will assess two different aspects of sensory function.

#### **MEASURE 1: LIGHT TOUCH FREQUENCY THRESHOLD**

Light touch is subserved by a group of myelinated peripheral nerves with fast conduction in the AB range and which are capable of following high frequencies, being responsible for the sensation of vibration. This capability of individual nerve fibers to respond with high frequency also underlies our ability to sense a light touch moving across the body surface as in brushing.

In preclinical studies we have shown that, following injury, these light touch fibers lose their ability to follow high frequencies and, in some cases, no longer respond to mechanical stimulation at all [1]. Oxytocin, when perfused around the neuronal cell

bodies of these A $\beta$  nerve fibers, partially restores their function, including their response to high frequency stimulation.

In order to determine the highest frequency that A $\beta$  nerve fibers can respond to, we have created a simple device that produces an oscillatory / vibratory stimulus which can be used on the hand. The subject places fingertips and volar aspect of the wrist sequentially and the device is set to slowly decrease the frequency of vibration from 1 kHz until the subject first perceives this. This is repeated three times at each site and takes under 5 minutes in total. More details are provided in the Appendix.

[figure not shown]
We anticipate that oxytocin will have no effect on normal A $\beta$  fibers and that this measure will not change after oxytocin administration. This will provide important data to contrast with the expected efficacy of oxytocin in the setting of injury, to be studied in subsequent protocols.

#### **MEASURE 2: SUSTAINED HEAT**

As part of a protocol used by us in several studies, the surface of the skin of the forearm or leg is heated to 45°C using an FDA approved, Peltier-controlled thermode for a period of 5 minutes (TSA®, Medoc, Ramat Yishai, Israel). This typically results in a slowly increasing pain experience, peaking at 5 minutes in the mild to low moderate range and has been tolerated by more than 150 subjects in studies over the past 14 years.

In an interim analysis of an ongoing clinical study in volunteers, we noted that spinal injection of oxytocin, 15  $\mu$ g (equivalent to 9 IU), that pain from this sustained heat was dramatically reduced over the 5 minutes of stimulus presentation (adjacent figure). In contrast, spinal oxytocin had no effect on the stimulus-response relationship of pain to noxious heat over a 42-50°C range when the stimuli were presented for only 5 seconds. These data suggest that oxytocin reduces C-fiber mediated signaling of sustained heat pain, likely through a spinal site of action.

Drugs administered spinally have a much higher

concentration in cerebrospinal fluid than plasma. Nonetheless, spinally administered drugs are typically absorbed to an extent and with a time course similar to that after intramuscular injection, and it is conceivable that the effect on sustained heat pain we are seeing in the spinal study reflect peripheral effects via systemic absorption. Thus, if we see a similar reduction in response to sustained heat in this protocol of intravenous administration, we will conclude that oxytocin is more likely acting peripherally than spinally.

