**Study Visit 1:** The participant will report to the Clinical Research Unit (CRU) or Piedmont Plaza II at least 1 day prior to study visit 2. The participant will review and sign the Informed Consent. After informed consent is adequately obtained, a detailed medical history will be obtained from the participant, female participants will have a urine sampled tested to determine pregnancy status. The research nurse will train the participants to estimate pain quantitatively using a 2 cm^2 Peltier controlled thermode (TSA®) applied to a forearm with 5 sec presentation of stimuli at 39, 41, 43, 45, 47, 49, and 50°C, using a 11 point numerical verbal scale (NRS) anchored at 0 for no pain and 10 for the worst pain imaginable. Typically, the participant is exposed to temperatures between 38° and 51° C using a random staircase method. After this training, we will ask them to report pain intensity on the 0-10 NRS scale every minute for 5 minutes upon exposure to a 4 cm^2 Peltier controlled thermode at 45°C. Finally, they will place first the fingertips of their hand and then the volar wrist, on a device and report when they first perceive a sensation as the surface vibration frequency declines from 1 kHz to 1 Hz. We have found this training session significantly reduces anxiety and variability in pain and hypersensitivity ratings on subsequent study days.

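### A similar fall in sustained-heat pain after IV oxytocin would not by itself establish a peripheral site of action, and the fall would have no concurrent control

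*Combined protocol and SAP*

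**What the plan says.** The section on Measure 2 (sustained heat) reports that spinal oxytocin strongly reduced pain from a 5-minute 45°C stimulus, had no effect on 5-second stimuli, and probably acted at a spinal site. It notes that spinally given drugs are far more concentrated in CSF than in plasma. It then allows that "it is conceivable that the effect on sustained heat pain we are seeing in the spinal study reflect peripheral effects via systemic absorption", and commits to a reading of the present study: on any "similar reduction in response to sustained heat in this protocol of intravenous administration, we will conclude that oxytocin is more likely acting peripherally than spinally".

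The Background describes the wider programme as IV infusions at locked plasma concentrations, "coupled with testing aimed to measure activity of oxytocin on peripheral nerves, in the spinal cord, and in the brain". Of the outcome it says "we plan to identify infusion regimens that only target 1 or 2 of these sites for clinical trials". Site selectivity under IV dosing is therefore still to be found.

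Under Protocol (Methods) and Study Visit 2, all subjects receive 10 IU IV over 10 minutes. Sustained heat is tested once before dosing and after the 30, 60, 120 and 180 minute blood samples. Five-second heat is tested before dosing and after the 60, 120 and 180 minute samples. No placebo, saline or untreated arm or period is described. At Visit 1 subjects practise the same tests; for sustained heat they "report pain intensity on the 0-10 NRS scale every minute for 5 minutes upon exposure".

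**The concern.** The sentence turns an effect seen after a systemic route into a statement about a peripheral site. Drug in plasma may act on peripheral nerve, cord or brain, and the Background treats all three as live possibilities. A similar fall would support the view that circulating oxytocin is enough to reduce sustained heat pain. That is a different claim from saying where it acts.

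The fall is also uncontrolled. Ratings of a repeated painful stimulus may change through habituation, expectation or time on the unit, and the design cannot separate these from drug effect.

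The Background calls the site of action critical to later trials and says these data support a grant application. Followed as written, the sentence could put a site conclusion into that application that this design does not support.

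**Working it through.** No figure in the plan bears on this point. The sample of 10 is a convenience sample, with no effect size, SD, alpha or power given for heat pain. The check is therefore mainly logical.

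**Route and site.** The conclusion is comparative, so ask how well each explanation predicts a similar fall after IV dosing.

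- *Peripheral action:* predicts it, if plasma exposure is adequate.
- *Spinal action:* predicts it less well if IV dosing puts little drug in CSF. The CSF-over-plasma premise points this way, but it is stated for spinal dosing only. No CSF level after IV dosing is given, and only venous blood is sampled. How much less well cannot be said.
- *Brain action of circulating drug:* also predicts it. The Background lists the brain as a site; the Measure 2 rule does not mention it.

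A similar fall can thus shift some weight from cord to periphery, by an unknown amount, and says nothing about periphery against brain.

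**Precision of the fall.** Input: n = 10 (Statistical Rationale). The half-width of the 95% interval for mean change at one test is t(0.975, 9)/√10 = 2.262/3.162 = 0.715 SD of the within-subject change.

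**Drift, illustration only.** The documents give no drift size and no numerical meaning for a similar reduction, and the figure with the spinal result is not in the text available to me. Assume no drug effect, a non-drug mean fall *d*, and a spinal effect *S*, both in SD units of the within-subject change. Assume a fall counts as similar if its 95% interval lies above 0 and contains *S*. With h = 2.262·s/√10, sample mean ~ N(d, 1/10) and 9s² ~ χ²(9), the probability is that of max(h, S − h) < mean < S + h, integrated over s:

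| S | d = 0 | d = 0.25 | d = 0.5 | d = 0.75 |
|---|---|---|---|---|
| 1.0 | 1.9% | 9.1% | 27% | 54% |
| 1.5 | 0.3% | 2.6% | 12% | 34% |
| 2.0 | <0.1% | 0.1% | 1.0% | 5.5% |
| 2.5 | <0.1% | <0.1% | <0.1% | 0.2% |

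Drift could mimic a moderate spinal effect but hardly one of 2 SD or more. The limit on what a fall says about site does not depend on any entry in this table.

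**Checks already in the design.**

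- Plasma samples precede 4 of 4 sustained-heat tests (30, 60, 120, 180 min).
- Five-second heat accompanies 3 of 4 (60, 120, 180 min). Since spinal oxytocin left brief heat unchanged, a fall in sustained heat alone would resemble the spinal pattern, and a fall in both would raise suspicion of drift. This check is absent at 30 minutes.
- Visit 1 offers one drug-free repeat, but the protocol reports that "this training session significantly reduces anxiety and variability in pain and hypersensitivity ratings on subsequent study days". A change from Visit 1 to the Visit 2 baseline reflects training, not drift within the day. It is also imprecise: a paired t-test with n = 10 (two-sided 5%) has power 0.803 for a 1.0 SD shift and 0.293 for 0.5 SD, so it misses the latter with probability 1 − 0.293 = 0.707.

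**The case against.** The strongest defence is that the sentence is hedged, conditional and limited to two explanations of an earlier result, and that it has a premise. Spinal dosing loads the CSF; if IV dosing without that load works as well, the spinal explanation loses ground. This stands in part. It would be wrong to infer that a similar fall could lend no support to a peripheral site. What it cannot do, without a CSF level after IV dosing and with the brain left out, is establish one.

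It can also be said that this is rationale for an added measure in a pharmacokinetic pilot, with no formal test attached, and that the Background leaves site identification to later work. That is true and limits the weight of the point. The sentence still commits the investigators in advance to a conclusion.

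Two stronger readings are tempting and are not supported:

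- *That 10 IU over 10 minutes reaches the cord or brain.* The documents leave this open. The reference list includes a primate study whose title reports oxytocin in CSF after IV dosing, but a title shows nothing about this dose in humans.
- *That the protocol undercuts its own comparison by saying "pharmacokinetics from intramuscular administration cannot alone inform computer controlled infusion of intravenous oxytocin".* That remark concerns programming an infusion pump. It is not about whether systemic absorption could explain the spinal result.

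Finally, an uncontrolled exploratory measure is an acceptable design choice for a pilot. The difficulty lies in the conclusion drawn from it.

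**Conclusion.** The point holds in a limited form. A similar fall after IV oxytocin would be consistent with systemic drug being sufficient to reduce sustained heat pain. It would not by itself establish a peripheral site, because CSF exposure after IV dosing is neither given nor measured, cord and brain action remain open, and there is no concurrent control.

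The precision figure (±0.72 SD) follows from n = 10 and a t interval. The drift probabilities rest on an assumed drift, spinal effect and definition of similarity. They show a range and are not an estimate of error in this study. A reader might infer from them that drift probably explains any fall. The documents do not support that: they give no drift size or direction, and they describe the spinal effect as dramatic.

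The sentence should be changed before the heat data are interpreted. The primary outcome, plasma oxytocin concentration, is unaffected.

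**What to change.** (a) Replace the concluding sentence of the Measure 2 section with: *a similar reduction would be consistent with systemic oxytocin being sufficient to reduce sustained heat pain; because there is no concurrent control and a central action of circulating oxytocin is not excluded, the result is exploratory and does not by itself identify the site of action.*

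(b) Report the sustained-heat change from baseline at 30, 60, 120 and 180 minutes with 95% intervals. Set it beside the paired plasma concentrations and the 5-second heat change at 60, 120 and 180 minutes. Label these comparisons descriptive and partial; a lag between plasma level and effect cannot be excluded. Show the Visit 1 to Visit 2 baseline change only as a check on training effects.

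(c) Separate and minor: Protocol (Methods) places heat training on the lateral calf, Study Visit 1 on a forearm, and Measure 2 allows forearm or leg. Reconcile these, and use one site for baseline and all post-dose tests.

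Cost: one sentence, one table from planned data and one named test site, with no new subjects, visits, samples or tests. The price is a weaker claim about site of action.

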## Protocol

### Pharmacokinetics of intravenous oxytocin and effects on sensory function in healthy volunteers

**PRIMARY GOAL:** Measure oxytocin in plasma after brief intravenous infusion and model its pharmacokinetics.

**METHODS:** Equal numbers of healthy adult men and women will be recruited (ten total). At least 1 day prior to study subjects will be trained to rate pain in response to heat applied to the lateral calf using a Peltier controlled thermode and to indicate when they first perceive a vibratory stimulus on the fingertips and wrist.

Subjects will return for study visit two in which an intravenous catheter will be inserted in the arm and, after baseline measures of response to heat and determination of vibration frequency threshold, subjects will receive oxytocin (Pitocin®), 10 IU over 10 minutes. Venous blood samples (5 ml) will be obtained before and at 2, 5, 10, 15, 30, 45, 60, 90, 120, 180, and 240 minutes after the end of the oxytocin administration by removal of blood from the intravenous catheter.

We will abandon an individual participant's study and schedule another participant should we be unable to successfully place the intravenous catheter.

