## **STUDY DESIGN**

**Inclusion Criteria:** We request permission to study up to 12 subjects so that we will have 10 evaluable subjects with complete sampling at all time periods.

1. Male or female  $\geq 18$  and  $\leq 60$  years of age, Body Mass Index (BMI)  $<40$ .
2. Generally in good health as determined by the Principal Investigator based on prior medical history, American Society of Anesthesiologists physical status I or II
3. Normal blood pressure (systolic 90-140 mmHg; diastolic 50-90 mmHg) resting heart rate 45-100 beats per minute) without medication
4. Female subjects of child-bearing potential and those  $< 1$  year post-menopausal, must be practicing highly effective methods of birth control such as hormonal methods (e.g., combined oral, implantable, injectable, or transdermal contraceptives), double barrier methods (e.g., condoms, sponge, diaphragm, or vaginal ring plus spermicidal

jellies or cream), or total abstinence from heterosexual intercourse for a minimum of 1 full cycle before study drug administration.

Exclusion Criteria:

1. Hypersensitivity, allergy, or significant reaction to any ingredient of Pitocin®
2. Any disease, diagnosis, or condition (medical or surgical) that, in the opinion of the Principal Investigator, would place the subject at increased risk (active gynecologic disease in which increased tone would be detrimental e.g., uterine fibroids with ongoing bleeding), compromise the subject's compliance with study procedures, or compromise the quality of the data
3. Women who are pregnant (positive result for serum pregnancy test at screening visit), women who are currently nursing or lactating, women that have been pregnant within 2 years
4. Subjects with neuropathy, chronic pain, diabetes mellitus, or taking benzodiazepines or pain medications on a daily basis.

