## **Study Visit 2**

On the second visit, the participant will report to the CRU, in the morning after having had nothing to eat or drink since midnight. A peripheral intravenous catheter will be inserted into a vein in an upper extremity and lactated Ringers solution infused at 1.5 ml/kg/hr for the duration of the study. After obtaining baseline measures (random presentation of 5 sec heat stimuli between 39 and 50°C, 5 minute presentation of a 45°C stimulus, and vibration frequency perception threshold as described in Visit 1), oxytocin (Pitocin®, 10 IU) will be administered intravenously over 10 minutes.

Venous blood will be sampled (5 ml) before the infusion and at 2, 5, 10, 15, 30, 45, 60, 90, 120, 180, and 240 minutes after oxytocin injection via the indwelling intravenous catheter. We will also repeat vibration frequency perception threshold in fingertips and wrist between the samples after samples at 5, 20, 45, 60, 120, and 180 minutes. In addition, we will ask them to rate pain intensity every minute for 5 minutes with a 45° stimulus after samples at 30, 60, 120, and 180 minutes (adjacent figure) and rate pain intensity to single, 5 second duration stimuli from 39°C to 50°C after samples at 60, 120, and 180 minutes as on the first visit.

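### Does central volume need a blood draw during, or exactly at the end of, the 10-minute oxytocin infusion?

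*Combined protocol and SAP*

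**What the plan says.** The combined protocol and SAP gives 10 IU intravenously over 10 minutes. The Methods paragraph of the Protocol section times the post-dose samples "at 2, 5, 10, 15, 30, 45, 60, 90, 120, 180, and 240 minutes after the end of the oxytocin administration", taken "by removal of blood from the intravenous catheter". That makes 11 post-dose draws, at 12 to 250 minutes from infusion start. Only one catheter is described, and under Study Visit 2 it also carries Ringer's solution throughout.

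Study Visit 2 lists the same times, ending "240 minutes after oxytocin injection via the indwelling intravenous catheter", without saying whether the clock starts at the beginning or the end of the infusion.

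On purpose, the section on other measures says that "the primary goal of this protocol is to model change in oxytocin concentrations in plasma after intravenous administration". Background looks ahead to "computer-controlled intravenous infusions of oxytocin to rapidly achieve and maintain targeted plasma concentrations". The section on why pharmacokinetics are needed adds "We cannot program infusion devices for targeted concentrations without knowledge of" oxytocin's pharmacokinetics, and says that virtually nothing is known of its "pharmacokinetics in this setting and nothing in the nonpregnant population".

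Study Design asks for up to 12 enrolled to obtain "10 evaluable subjects with complete sampling at all time periods". Statistical Rationale names plasma concentration at defined times after the infusion as the primary outcome. It calls the 10 subjects a convenience sample for variance estimates, which will support either use of these parameters or a proposal for a larger sample.

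**The concern.** A targeted infusion opens with a step scaled to the central volume (V1), and an error in V1 carries over in proportion to the first concentration reached. V1 is seen most directly while drug is going in or has just stopped. The first draw comes 2 minutes after stop, so if the fast phase is short, much of it is over by then.

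Because the documents say nothing is known in this population, the schedule cannot rely on a slow fast phase. If subjects are fitted one at a time and the estimates pooled, V1 estimation error would also pass as between-subject variation, which is the quantity Statistical Rationale wants for planning. One extra or moved draw appears to be a cheap cure.

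**Working it through.** The plan states no precision figure, half-life, compartment structure, assay error or fitting method, so there is nothing to reproduce. Every result below is conditional on assumptions.

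**Inputs from the documents.** 10 IU over 10 minutes; the sampling times above; 10 subjects. Measure 2 equates 15 µg with 9 IU, so 10 IU = 10 × 15/9 = 16.7 µg, or R = 1.667 µg/min.

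**Assumed.** Two compartments (CL, V1, Q, V2), baseline 2 pg/mL, error variance (0.15·C)² + 0.5², instant mixing, and arm venous plasma tracking the central compartment.

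**How much of the fast phase is left.** The fraction of the fast component remaining t minutes after stop is 2^(−t/h):

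| Fast half-life h | +2 min | +5 min | +10 min | +15 min |
|---|---|---|---|---|
| 1.5 min | 0.40 | 0.10 | 0.01 | 0.001 |
| 3 min | 0.63 | 0.31 | 0.10 | 0.03 |
| 10 min | 0.87 | 0.71 | 0.50 | 0.35 |

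**Precision of V1.** With g_j the gradient of C(t_j) in the log parameters (CL, V1, Q, V2, baseline), the information is M = Σ g_j g_jᵀ / var_j, and CV(V1) = √[M⁻¹] at the V1 entry. In each alternative the 90-minute draw is replaced.

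| Set: CL L/min, V1 L, Q L/min, V2 L | Fast half-life (min) | Planned | Mid-infusion | At end | 1 min after stop |
|---|---|---|---|---|---|
| A: 1, 5, 1, 10 | 1.5 | 129% | 32% | 43% | 76% |
| E: 1.2, 8, 0.3, 5 | 3.4 | 31% | 18% | 21% | 24% |
| B: 1, 10, 0.5, 10 | 4.1 | 32% | 18% | 21% | 24% |
| C: 0.6, 8, 0.4, 30 | 5.3 | 21% | 14% | 15% | 16% |
| F: 1, 15, 0.3, 10 | 7.2 | 20% | 14% | 15% | 16% |
| D: 1, 20, 0.3, 20 | 10.0 | 14% | 11% | 12% | 12% |

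A CV above 100% means only that V1 is not identifiable from one subject. A wider grid (slow half-life 10 to 60 minutes, 15% proportional error) gives median CVs, planned to mid-infusion, of 41% to 19% at 3 minutes and 24% to 15% at 5 minutes. With one-compartment disposition the gain is smaller: 18.5% to 12.8% at 3 minutes.

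**What this does to a 10-subject summary.** Take an assumed 30% between-subject SD and subject-by-subject fitting. The apparent SD is √(0.30² + CV²), and the standard error of the mean is that divided by √10.

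- 3 minutes, planned: √(0.09 + 0.168) = 51%, SE 16.1%. With a mid-infusion draw: √(0.09 + 0.036) = 36%, SE 11.2%.
- 5 minutes, planned: √(0.09 + 0.058) = 38%, SE 12.1%. With a mid-infusion draw: √(0.09 + 0.0225) = 34%, SE 10.6%.
- Floor with V1 known exactly: 30%/√10 = 9.5%.
- An SD from 10 subjects has a relative error of about 1/√(2·9) = 24%.

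**Robustness of the remedies.** With an unmodelled 1-minute venous lag, noise-free fits of set B bias V1 by about +10% to +15% with the mid-infusion draw and +2% to +4% with the end draw, depending on weighting. The better of the two therefore depends on an unknown. For a single-line draw 1 minute after stop, 20% carry-over in that one sample shifts V1 by roughly −7% to −50% across the six sets. That carry-over is only about 1 ng of a 16.7 µg dose, and its likely size cannot be worked out because neither infusion volume nor line dead space is given.

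**The clock.** If Study Visit 2 were read from infusion start, V1 CV for A to D would be 21, 13, 10 and 9%, but Q would be less precise in four of the six sets (B 23.4% to 32.6%, for example). Methods states the origin outright; Study Visit 2 merely omits it.

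**The case for a change.** The best case for a change is that the schedule should withstand a short fast half-life precisely because nothing is known. A mid-infusion draw improved V1 in every parameter set tried. A swap keeps 12 draws and 60 mL, and an added draw costs 5 mL and one assay. If the model is right, an added draw cannot lose information. The planned schedule is not immune to venous lag either: a 1-minute lag biases V1 in set B by about −14%.

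Most of this stands. V1 would be better determined with an infusion-phase draw, and materially so if the fast half-life is about 3 minutes or less. What does not stand is that the draw is cheap. Blood taken through the line delivering oxytocin would be contaminated, so a draw during the infusion or exactly at its end needs in practice a second cannula. That adds pain, bruising and another chance of failed placement, when 12 − 10 = 2 losses are all the plan allows. The one-line alternative exchanges variance for a carry-over bias of unknown size. A swap also removes the sample that closes the interval after the 60-minute sensory tests.

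The variance-inflation argument further requires subject-by-subject fitting, which the documents do not specify. A mixed-effects model would separate estimation error from between-subject variation, although V1 would still rest on few informative draws.

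**Conclusion.** No change follows. The sampling gap is a design trade-off and not an error. Its cost ranges from slight (fast half-life of 5 minutes or more, per-subject V1 CV about 25% or less) to serious (below about 2 minutes, V1 not identifiable from one subject). The documents do not say where oxytocin lies in that range. The primary outcome, concentrations at defined times after the infusion, is unaffected, and Statistical Rationale already allows for a larger sample if these parameters prove too imprecise. Avoiding a second cannula is reasonable for a 10-subject preliminary study.

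The looser time origin in Study Visit 2 is a clerical slip, since Methods fixes it at the end of the infusion; the two should be read together on that clock. Recording actual draw times and fitting to them is what a pharmacokinetic analyst would do anyway. This conclusion rests on an assumed two-compartment model, 15% proportional error, and venous plasma that tracks the central compartment closely.
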